12.2. DATA REPORTING AND TRANSFER

For each database provided in the table above, please indicate the ability to export individual-level reports to an Excel or comma-delimited format and whether identifying information is available for linking to data from other sources.

Database Name	Ability to Export Individual Reports?	What identifying information is available to facilitate linking to other data sources?
nFORM	Yes, pre-packaged operational reports, excel, cvs, tab delimited	Name, DOB, nFORM ID
Qualtrics	Yes, Excel, cvs, tab delimited, others	Name, DOB, nFORM ID

* you may add rows by hitting the tab button, or right click and select insert row below

12.3. CURRENT SECURITY AND CONFIDENTIALITY STANDARDS

For each database provided in Section 11.1, please Indicate the ability to be able to encrypt data access during transit (for example, accessed through an HTTPS connection); be able to encrypt data at rest (that is, when not in transit), have in place a data backup and recovery plan; require all users to have logins and passwords to access the data they are authorized to view; and have current anti-virus software installed to detect and address malware, such as viruses and worms.

Database Name	Ability to encrypt data during transit?	Ability to encrypt at rest?	Data Backup and Recovery Plan?	Require all users to have logins and passwords?	Current Anti-Virus Software Installed?
nFORM	Yes	Yes	Yes	Yes	Yes
Qualtrics	Yes	Yes	Yes	Yes	Yes

* you may add rows by hitting the tab button, or right click and select insert row below

Please describe any plans for study registration with an appropriate registry (e.g., clinicaltrials.gov, socialscienceregistry.org, osf.io, etc.).

This study will be registered with clinicaltrials.gov.

TYRO Champion Dads

Statistical Analysis Plan

12/9/2024

Clinicaltrial.gov ID:
NCT05256992

1. Data Analysis

Briefly describe the planned approach for data analysis. If an impact analysis is proposed, name the key dependent and independent variables, and describe any methods to minimize Type I error (i.e., finding positive impacts by chance) such as limiting the number of impacts to be analyzed and/or multiple comparison correction. Describe proposed approach(es) for addressing missing data.

Identify impact study sample

The impact study sample includes participants who: 1) were eligible to be randomized based, 2) gave recorded informed consent to be part of the study and randomly assigned to a treatment group, and 3) took both an entrance and exit and/or follow-up survey. The CONSORT diagram in Appendix A shows exclusion criteria and the anticipated size of the overall impact study sample, which we anticipate to differ for attitudinal items that will use wave 2 data vs behavioral questions that will use wave 3 data. The analytic sample for particular outcome measures will vary based on missing data.

Defining analysis measures

For each outcome construct, we have identified the relevant measures from nFORM that are theoretically aligned with that construct. We will generate a correlation matrix between items in a given construct to ensure that theoretically related items are also empirically related in our data set. Items that are not strongly correlated with other items in a construct will be removed as necessary. Factor analysis will be used to ensure that all construct items hang together (using an alpha of 0.7 or higher as the threshold).

Once we are confident that all of the items align with a given construct, we will create a composite measure by taking an average of the scores on each non-missing item in the construct. The measure definition matrix below provides information on each proposed outcome measure.

For the sake of consistency and simplicity, parenting and co-parenting analyses will use a participant's youngest child as the focal child.

Measure	Sample	Variable Type	Data source(s)	Variable Name	Definition
Co-parenting relationship behaviors	Has at least one child age 24 or younger	Continuous (range from 1 to 5 where 1 is strongly disagree and 5 is strongly agree)	nFORM entrance, OLLE follow-up	Copar_Beh	Average of 11 survey items that relate to positive interactions with the mother of participant's youngest child

Parenting relationship behaviors	Has at least one child age 24 or younger, saw child within past month	Continuous (range from 1 to 5 where 1 is never and 5 is every day or almost every day)	nFORM entrance, OLLE follow-up	Par_Beh	Average of 10 to 11 survey items (depending on child age) that relate to frequency of positive interactions with participant's youngest child
Parenting relationship attitudes	Has at least one child age 24 or younger, saw child within past month	Continuous (range from 1 to 5 where 1 is always and 5 is never)	nFORM entrance, nFORM exit	Par_Att	Average of 6 survey items that relate to frequency of feelings about participant's youngest child
Parenting relationship behaviors	Has at least one child age 24 or younger, saw child within past month	Continuous (range from 1 to 5 where 1 is never and 5 is every day or almost every day)	nFORM entrance, OLLE follow-up	Parent_Fight	Reported frequency of fighting with child
Partner relationship behaviors	All survey respondents	Continuous (range from 1 to 5 where 1 is never and 5 is always)	OLLE pre-survey, OLLE post-survey, OLLE follow-up	Partner_Fight	Reported frequency of fighting with partner
Partner relationship behaviors	All survey respondents	Continuous (range from 1 to 5 where 1 is never and 5 is always)	OLLE pre-survey, OLLE post-survey, OLLE follow-up	Partner_Disagree	Average of 7 survey items related to frequency of disagreement with partner on different topics

Analytic approach

The main goal of this impact study is to assess the impact of the addition of the Ray of Hope curriculum intervention on participant attitudinal outcomes immediately following program completion, and behavioral outcomes six months after program enrollment, as compared to the impact of standard TCD services alone.

Participation benefits are defined by the primary and secondary outcomes presented earlier in the theory of change logic model and with research questions and hypotheses. Impact estimates are based on participant responses to the OLLE Follow-up Survey across randomly assigned study groups to compare primary and secondary outcomes between them 6-months after TCD Project enrollment. More positive outcomes for the treatment group will be attributed to the intervention given that other TCD services are delivered in the same ways to both study groups under a shared condition.

Steps begin by creating constructs that serve as the dependent variables used to model comparisons of primary outcomes—parent, co-parent, and partner relationship behaviors—and secondary outcomes—parenting attitudes. Constructs are comprised of the relevant survey items on the nFORM Community Fathers Survey and the OLLE Survey. Constructs are confirmed with psychometric evidence derived from confirmatory factor analysis (CFA), except when they are already supported by evidence of reliability and validity or based on one item that is sufficiently broad to investigate an outcome. Next, results from baseline equivalency analyses identify co-variates to specify in the model that control for any detected differences in participant characteristics or developmental starting points in healthy family relationships and economic stability. Model results are interpreted to determine if assignment to the treatment group positively predicts ($p < .05$) more improved outcomes than the control group 6-months after enrollment into TCD services for behavior outcomes and immediately following program completion for attitudinal outcomes.

Finally, type 1 and type 2 error are controlled in this study. Type I error is the rejection of a true null hypothesis (also known as a "false positive" finding or conclusion; example: "an innocent person is convicted"). We control for type 1 error in two ways. First, alpha levels are set at .05, so only 1 in 20 findings should result in a false positive, and we plan to use the Bonferroni correction method to adjust for multiple hypothesis tests. Second, research questions are limited to modeling six outcomes. Type II error is the non-rejection of a false null hypothesis (also known as a "false negative" finding or conclusion; example: "a guilty person is not convicted"). We control for Type 2 error by having sufficient power to detect small or nearly small minimum detectable effect sizes. (The estimated effect sizes are all almost small effects that would be detected, based on best practices outlined by Cohen (1988) of small effect sizes <0.02 and medium effect sizes <0.15 .)

Chi-Square and 2-sample t-tests assess baseline equivalency of study groups by analyzing pre-survey responses to items that describe the characteristics of participants and their developmental starting points before receiving TCD services. Participant characteristics—such as demographics, family structure, and socioeconomic background—are reported on the nFORM ACS Survey. Developmental starting points refer to the attitudes and behavior exhibited before TCD participation and are reported on the nFORM Community Fathers Entrance Survey and OLLE Pre-survey. Chi-Square tests are run for

categorical and dichotomous variables, such as relationship status (e.g., married, single, divorced) or whether a participant reports having a savings account (i.e., yes/no). Two-sample t-tests are run for interval and continuous variables, such as the number of children in a household, or levels of agreement with healthy parenting attitudes. Any differences detected across study groups are incorporated into the model as co-variates.

Study group assignment (1=treatment, 0=control) is repeatedly regressed against the dependent variables to model comparisons of outcomes constructs between study groups (see the table below). Co-variates specified in the model will control for the influence of any significant baseline differences between study groups that were detected in the baseline equivalency analyses for demographics, family structure, socioeconomic background, and developmental starting points.

Procedures to run the linear regression model rely on standard regression to model the influence of study group assignment on dependent variables. All dependent variables are continuous, such as when participants report how many hours they spend with their child or respond to multiple items in a scaled construct by indicating levels of agreement with statements about key parent attitudes.

Benefits of the Ray of Hope curriculum will confirm hypotheses if respondents assigned to the treatment group report greater improvements in outcomes ($p < .05$) than those in the control group for each outcome measure identified above.

For the implementation analysis, program fidelity will be descriptively reported by the percentage of enrolled participants who receive: 1) any primary workshops, 2) employment supports, 3) substantive service contacts, 4) referrals. The program aims to provide all participants each of these four program components, so the percentage of participants who receive each of these will be compared to the 100% benchmark. Number of substantive service contacts per participant will also be compared to the benchmark of 8 SSCs set by OFA for FIRE grantees.

Dosage will be measured by percent of target primary workshops participants attend on average (using 90% as a benchmark), and categories of attendance (initial, halfway, 90%, 100%) will be reported and compared to targets established by the program.

Handling missing data

Outcomes

When creating the composite measures for our behavior and attitude outcomes, we will create a composite score by taking the average of multiple individual items. For these measures, our current plan is to use 20% as a threshold for allowable missing items, based on guidance from evaluation technical assistance resources. This plan is contingent on the final distribution of missing data in our data set. If participants have more than 20% of items missing for a given construct, the respondent will be assigned a missing value for that construct and will be excluded from the analytic sample for that outcome. We will not be imputing truly missing values for outcomes. To create a construct score, the average will divide by the number of non-missing values in the construct.

For outcomes that use single survey items, participants who do not respond to that item on either the pre- or follow-up survey will be excluded from the analytic sample for that outcome.

Data for the implementation outcomes could be missing as a result of programmatic data entry issues. For the sake of this evaluation, we assume that any primary or support services received by a participant are being accurately logged into nFORM, so a lack of documented attendance, service contacts, referrals, etc. is indicative of lack of services (i.e., a participant not receiving the program components as intended).

Assessing non-response bias

We will conduct response rate analysis for each primary outcome of interest to assess non-response bias and adjust for threats to internal validity. Using data from the Applicant Characteristics Survey, we will look at demographics (race, ethnicity, age, education level) and primary reason for joining the program among participants who fall into each of the following categories: 1) non-respondents who answered no surveys after the ACS, 2) respondents who completed a pre-survey only, and 3) respondents who completed both a pre- and follow-up survey (complete case). We will also look for differential response rates between the standard/control and enhanced/treatment groups.

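### The SAP drops randomised fathers with an observed outcome when the baseline survey or single item is missing, although its regression uses that value only if the arms differ on it

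*SAP*

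**What the plan says.** Under the SAP heading Identify impact study sample, the third condition for inclusion is that the father "took both an entrance and exit and/or follow-up survey". An entrance survey is thus required whatever was observed later.

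Under Handling missing data (Outcomes), the rule for single-item outcomes is that "participants who do not respond to that item on either the pre- or follow-up survey will be excluded from the analytic sample for that outcome". This covers Parent_Fight and Partner_Fight. For the four composites the rule is "If participants have more than 20% of items missing for a given construct, the respondent will be assigned a missing value for that construct", with exclusion from that outcome. No survey wave is named there. The section adds "We will not be imputing truly missing values for outcomes" and says nothing about missing baseline values or covariates.

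Under Analytic approach, "Study group assignment (1=treatment, 0=control) is repeatedly regressed against the dependent variables". Baseline variables come in through one route: "Any differences detected across study groups are incorporated into the model as co-variates". The next paragraph repeats this: "Co-variates specified in the model will control for the influence of any significant baseline differences between study groups". No change score is defined, and the baseline outcome is not a fixed covariate.

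Under Assessing non-response bias there are three groups: no survey after the Applicant Characteristics Survey, pre-survey only, and "3) respondents who completed both a pre- and follow-up survey (complete case").

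**The concern.** A father who consented, was randomised and answered at exit or six months has supplied what the comparison of arms needs. Removing him because an earlier survey is absent discards an observed outcome and moves the analysed groups further from the groups as assigned. The ban on imputing outcomes does not justify this, since his outcome is present.

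The response analysis has no group for a father with an outcome survey and no pre-survey, so the loss would not appear as a separate count either.

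Precision is at stake in a trial that already plans to lose 30% of those randomised. So, conditionally, is balance between the arms.

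**Working it through.** **Is the baseline value needed?** Setting the SAP sections side by side:

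- The impact-sample rule always requires the entrance survey.
- The regression uses a baseline score only if the equivalency tests find a difference on it. Where none is found, a father is excluded for lacking a value that the model does not contain.
- Demographics, family structure and socioeconomic background come from the Applicant Characteristics Survey, which is a separate instrument. Those covariates may exist without an entrance survey.
- In the measures table (Protocol 10.1, repeated in the SAP), both partner outcomes draw only on the OLLE pre, post and follow-up surveys. If entrance means the nFORM entrance survey, a father with complete OLLE partner data could still be dropped.

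**Where is the exclusion explicit?** At survey level, it follows from the entrance-survey condition. At item level, it is explicit for Parent_Fight and Partner_Fight only. For Copar_Beh, Par_Beh, Par_Att and Partner_Disagree, the 20% rule could refer to the outcome wave, the baseline wave or both.

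**Reproducing the design figure.** Inputs from Protocol 9.2 and 9.3: 443 per arm randomised, 310 per arm analysed, one-tailed 0.05, 80% power, effect size 0.2.

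- Loss: 1 − 310/443 = 30.0%. No part of it is set aside for missing baseline.
- MDES = (1.645 + 0.842) × √(2/n). At n = 310 this is 0.1997, which matches the stated 0.2.
- Power at 0.2 SD with 310 per arm is 80.1%.

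**Size of the effect.** The documents give no rate of missing baseline among fathers with an outcome, so the rates below are assumptions.

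*If 310 is already net of the rule*, keeping more fathers gives:

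| Extra fathers kept (assumed) | n per arm | MDES |
|---|---|---|
| 0% | 310 | 0.1997 |
| 5% | 325.5 | 0.195 |
| 10% | 341 | 0.190 |
| 15% | 356.5 | 0.186 |

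*If 310 instead counts all fathers with an outcome*, the rule cuts into it:

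| Missing baseline (assumed) | n per arm left | Fathers lost, both arms | Power at 0.2 SD | MDES |
|---|---|---|---|---|
| 2% | 304 | 12 | 79.4% | 0.202 |
| 5% | 294 | 31 | 78.3% | 0.205 |
| 10% | 279 | 62 | 76.3% | 0.211 |
| 15% | 264 | 93 | 74.2% | 0.217 |

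**Bias.** If a fraction b of an arm is dropped and those fathers differ from the retained ones by g SD, the arm mean shifts by b × g. The treatment difference shifts by (b_T − b_C) × g when g is the same in both arms.

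- Equal loss of 5% and g = 0.3: shift 0.
- Assumed loss of 10% against 5%, g = 0.3: 0.05 × 0.3 = 0.015 SD.
- The same losses with g = 0.5: 0.05 × 0.5 = 0.025 SD.

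The last two are 7.5% and 12.5% of the 0.2 SD target. They are illustrations only.

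**Could the loss differ by arm?** Protocol 7.1 places randomisation after documented consent and tells fathers their assignment at once. Protocol 10.3 allows baseline collection up to the first primary workshop session. The order of the two is not fixed, so baseline completion may follow knowledge of assignment.

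**The case against.** **The number may be very small.** Protocol 10.3 has the CQI Data Manager proctor the baseline surveys and help participants, close to enrolment. Protocol 10.4 says exit surveys reach mainly those who finish the program and attend the last session. Few fathers should have an exit survey and no entrance survey. This stands. The SAP also refers to a CONSORT diagram in its Appendix A, which was not in the text available for this check and may give counts.

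**The baseline value may be needed after all.** Most outcome rows pair a baseline source with a later one, and the SAP says the hypotheses are confirmed by greater improvements in the treatment arm. A reader could take that as change from baseline. The SAP defines no such score. Even if adjustment for baseline is meant, that calls for a way to handle a missing covariate and does not require removing the father.

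**Requiring a baseline lets equivalence be checked on the fathers analysed.** That is a real advantage of a complete-case set. It supports keeping that set as a sensitivity analysis.

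**The plan already looks at response.** It does plan response-rate analysis and a comparison of response rates by arm. The missing group remains a gap in that analysis.

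**Stronger readings that a reader might infer.** One is that skipping any single pre-survey item removes a father from every outcome. The text does not say so: the item rule is explicit for two of six measures, and one missing item would not normally breach a 20% limit. Another is that the rule biases the results. Nothing in the documents shows that baseline loss, or its link to outcome, differs by arm.

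**Conclusion.** The point holds within limits. Followed as written, the SAP excludes randomised fathers whose outcome was observed: at survey level through the entrance-survey condition, and at item level for Parent_Fight and Partner_Fight. For the composites the wave is unstated. The stated regression does not require this exclusion.

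The size cannot be known from the documents. The improvement in MDES from 0.200 to between 0.195 and 0.186 rests on two assumptions: that 5% to 15% more fathers would be kept, and that 310 per arm is already net of the rule. Bias is possible and not demonstrated. Loss at exit and follow-up may well be the larger problem. The change is still worth making, because it keeps the analysis closer to the groups as assigned at almost no cost.

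**What to change.** 1. Define the primary analysis set for each outcome as all consented, randomised fathers with that outcome observed at its relevant wave: exit for Par_Att, six-month follow-up for the behaviours.
2. Remove the pre-survey from the single-item exclusion rule, and state which wave the 20% composite rule covers.
3. Where a baseline covariate is in the model and missing, keep the father by a prespecified method, for example filling in the mean pooled over arms. Add a missing-value indicator only if baseline missingness is shown not to differ by arm. Baseline may follow disclosure of assignment, so the indicator could otherwise be a post-assignment variable. Report an unadjusted estimate alongside.
4. Add a group to the response analysis for fathers with an exit or follow-up survey and no pre-survey, reported by arm.
5. Keep the set with both surveys as a sensitivity analysis.

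The cost is SAP wording, a few lines of code and slightly more analysis. No new data are needed. The one drawback is that baseline equivalence can then be checked only on those analysed fathers who have a baseline.

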3. EVALUATION ENROLLMENT

Please provide the expected start and end dates for program and evaluation enrollment using the tables below. For impact studies, please indicate expected start and end dates for each study group.

IMPLEMENTATION EVALUATION		
Please leave blank if not conducting an implementation study.		
	Program Enrollment	Study Enrollment
Start Date	04-01-2021	05-20-2022
End Date	03-01-25	03-01-25
Definition	
Fathers who are 18+ years of age, have no open criminal cases (can be deferred), with children up to 24 years old
	
Fathers who are 18+ years of age, have no open criminal cases (can be deferred), with children up to 24 years old AND agree to participate in the study after informed consent

IMPACT EVALUATION			
Please leave blank if not conducting an impact evaluation.			
	Program Enrollment	Study Enrollment	
		Treatment Group	Comparison Group
Start Date	04-01-2021	05-20-2022	05-20-2022
End Date	06-30-2025	11-30-2024	11-30-2024
Definition	
Fathers who are 18+ years of age, have no open criminal cases (can be deferred), with children up to 24 years old
	
Fathers who are 18+ years of age, have no open criminal cases (can be deferred), with children up to 24 years old AND agree to participate in the study after informed consent AND were not referred to the program due to involvement in a domestic violence case
	
Fathers who are 18+ years of age, have no open criminal cases (can be deferred), with children up to 24 years old AND agree to participate in the study after informed consent AND were not referred to the program due to involvement in a domestic violence case

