1.2. OUTCOME RESEARCH QUESTIONS

For each outcome research question listed above, whether a descriptive or impact design, summarize the inputs (e.g., program components, program supports, implementation features, etc.), target population (e.g., the population for which the effect will be estimated) and the outcomes (e.g., child well-being, father-child engagement, etc.) that will be examined to answer the research question(s). Comparisons for descriptive evaluations may reflect circumstances before the grant, pre-treatment, or pre-determined benchmark from other studies with similar interventions.

Research Question Number	Intervention	Target Population	Comparison	Outcome	Confirmatory or Exploratory?
R1	Ray of Hope curriculum (10 hours) that focuses on domestic violence and related risk factors	Latino fathers: low-income, 18+ years, no open criminal cases (or deferred), children up to 24 years	Parenting attitudes for the treatment group to the control group immediately after completing TCD program.	Healthier parenting attitudes for the Treatment Group that receives enhanced services.	Confirmatory
R2	Ray of Hope curriculum (10 hours) that focuses on domestic violence and related risk factors	Latino fathers: low-income, 18+ years, no open criminal cases (or deferred), children up to 24 years	Partner relationship behaviors for the treatment group to the control group 6 months after TCD enrollment.	Healthier partner relationship behaviors for the Treatment Group that receives enhanced services.	Confirmatory
R3	Ray of Hope curriculum (10 hours) that focuses on domestic violence and related risk factors	Latino fathers: low-income, 18+ years, no open criminal cases (or deferred), children up to 24 years	Parenting behavior for the treatment group to the control group 6 months after TCD enrollment.	Healthier parenting behavior for the Treatment Group that receives enhanced services.	Confirmatory
R4	Ray of Hope curriculum (10 hours) that focuses on	Latino fathers: low-income, 18+ years, no open criminal	Co-parenting behavior for the treatment group to the	Healthier co-parenting behavior for the Treatment	Confirmatory

	domestic violence and related risk factors	cases (or deferred), children up to 24 years	control group 6 months after TCD enrollment.	Group that receives enhanced services.	
--	--	--	--	--	--

* you may add rows by hitting the tab button, or right click and select insert row below

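### Parent_Fight pools youngest children from infancy to 24 years with no planned adjustment for child age, which costs some power but does not bias the comparison; an age-band covariate should be prespecified

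*SAP*

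**What the plan says.** In SAP section 1, the measure matrix defines Parent_Fight as "Reported frequency of fighting with child". It is one item with "range from 1 to 5 where 1 is never and 5 is every day or almost every day", and the sample is any father who "Has at least one child age 24 or younger, saw child within past month". Protocol section 10.1 has the same row. Under Defining analysis measures, the SAP states that "parenting and co-parenting analyses will use a participant's youngest child as the focal child". Eligibility in Protocol section 3 is worded as fathers "with children up to 24 years old", with no minimum child age.

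Par_Beh has the same construct label as Parent_Fight, and its number of items (10 or 11) depends on the child's age. The Parent_Fight row says nothing about age.

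Under Analytic approach, each outcome is regressed on study group. Covariates enter only if the baseline equivalency tests detect a difference between arms. For single-item outcomes, the missing-data rule is that "participants who do not respond to that item on either the pre- or follow-up survey will be excluded from the analytic sample for that outcome". The R3 outcome in Protocol section 1.2 is "Healthier parenting behavior for the Treatment Group that receives enhanced services", marked confirmatory. No table maps variables to research questions, so Parent_Fight is tied to R3 only by its label.

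**The concern.** How often a father fights with his child is likely to depend strongly on the child's age. With the youngest child as focal child and no lower limit, the analysis can combine infants, school-age children and young adults in one linear model. Fathers of very young children plausibly score 1, the best possible value, whatever their arm. This has two effects:

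- These fathers contribute little or no treatment effect, so the average difference between arms shrinks.
- The gap between them and the other fathers adds variance unrelated to treatment.

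The covariate rule does not deal with the second effect. Randomisation tends to balance child age, so the baseline tests would usually find no difference and child age would stay out of the model. The Protocol's power table assumes that all 620 analysed fathers can contribute the full 0.2 SD to parenting behavior. What is at stake is the chance of missing a real reduction in fighting among fathers of older children.

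**Working it through.** **Inputs from the documents (Protocol section 9.3).** 620 analysed, taken as 310 per arm; one-tailed 0.05; 80% power; minimum detectable effect size 0.2.

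**Reproducing the plan's figure.** (1.645 + 0.842) × √(2/310) = 0.1997, and power at 0.2 SD is 80.1%. The stated 0.2 is confirmed, if every father can contribute.

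**Assumed inputs, because the documents give none.**
- A share f of each arm scores 1 at follow-up in both arms, with no variance and no effect.
- The remaining fathers have mean 2, SD 1 and a true effect of 0.2 SD. Let m = (mean − 1)/SD, here 1.
- The follow-up score is analysed without baseline adjustment.
- The age band separates the two groups cleanly.

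**Unadjusted analysis.**
- Overall effect = 0.2(1 − f).
- Overall SD = √[(1 − f) + f(1 − f)m²].
- Power = Φ(effect/SD × √(310/2) − 1.645).

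At f = 20%: effect 0.16; SD = √(0.80 + 0.16) = 0.980; standardised effect 0.163; z = 0.163 × 12.45 = 2.03; power 65.1%.

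**With the age band as covariate, all fathers kept.** The coefficient still estimates 0.2(1 − f). The band removes the between-group term f(1 − f)m², which leaves residual variance (1 − f). So z = 0.2 × √[(1 − f) × 155]. At f = 20%: 0.2 × √124 = 2.23; power 72.0%. Excluding the floor group gives the same z, so nobody has to be dropped to obtain the gain. The ratio of the two z values is √(1 + f·m²), which is never below 1.

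| f | Standardised effect, unadjusted | Power, unadjusted | Power, age band | Gain (points) |
|---|---|---|---|---|
| 10% | 0.181 | 72.8% | 76.3% | 3.5 |
| 20% | 0.163 | 65.1% | 72.0% | 6.9 |
| 30% | 0.147 | 57.2% | 66.9% | 9.7 |

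**Sensitivity to the assumptions.**
- With mean 1.5 and SD 0.8 in the remaining fathers, unadjusted power is 74.9%, 69.1% and 62.8%. Power with the band is unchanged, so the gains are 1.4, 2.9 and 4.1 points.
- If change from baseline is analysed, floored fathers contribute zero change, and (mean − 1) is replaced by the mean change in the other fathers. If that is near zero, the covariate gains almost nothing. Adjusting for the baseline score would likewise absorb part of the variance.
- All these figures use an uncorrected 0.05. With the SAP's planned Bonferroni correction over six outcomes (one-sided 0.05/6), power is already 54% with no floor. At f = 20% and m = 1 it is about 36% unadjusted and 43% with the band.

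**If the survey skips the item for young children.** Those fathers would be missing and, under the single-item rule, excluded. There would then be no floor, but the n for this outcome would be below 620. At 20% skipped, 248 per arm remain and power is again 72.0%.

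**The case against.** The strongest reply is that the floor is inferred. The documents give only a short label for the item, not its wording, response options or routing. The age-dependent item count in Par_Beh fits an instrument that routes by age as well as it fits an oversight. The share of very young focal children is also unknown. All of this stands. A reader might infer that fathers of infants sit at *never* by construction and that the measure cannot show a benefit in them. The documents do not support that. Follow-up comes about six months after enrollment, when each child is older. A father at *never* at baseline can rise from it, and treatment could show as a smaller rise.

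It can also be said that an average over all ages is the effect in the stated target population, and that an age cut-off would narrow that population at a threshold with no basis in the documents. That stands too. It argues against exclusion as the main analysis, but not against a covariate that keeps every father.

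Finally, part of the loss cannot be recovered. At f = 20%, power falls by 15.0 points (80.1% to 65.1%) and the covariate restores 6.9. The gain is modest, and close to nothing if change is analysed. What remains is that the SAP states no age rule for this item, and its covariate rule would usually omit a likely strong predictor.

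**Conclusion.** The point holds as a modest loss of efficiency. The focal-child rule, the missing lower age limit and the covariate rule are all in the text. The floor, its size and the share of fathers affected are assumptions. For 10% to 30% at the floor, with mean 2 and SD 1 in the rest and an unadjusted follow-up score, power falls from 80% to between 73% and 57%. An age-band covariate brings it to between 76% and 67%.

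A reader might go further and conclude that the arm comparison is biased or that R3 fails. Neither follows. Randomisation balances child age in expectation, so the effect is dilution. Parent_Fight can still show a benefit overall, and R3 does not rest on this item alone because Par_Beh has the same label.

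**What to change.** - Keep fathers of children of all ages in the main Parent_Fight analysis.
- Prespecify a baseline focal-child age band as a fixed covariate in that model, whether or not the arms differ on it. Choose the bands from baseline ages pooled over arms, before outcomes are seen by arm.
- Report the Parent_Fight result by age band as a supporting analysis.
- State the item wording, any age skip, and the resulting n for this outcome.
- Do not make an age cut-off exclusion the main analysis.

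The cost is a few lines in the SAP and a few degrees of freedom. Child age should already be on file, since the plan needs it to identify the youngest child and to select the Par_Beh items. No father is dropped and the target population is unchanged. The SAP is dated 12/9/2024 and the Protocol schedules follow-up surveys to 05/31/25, so the change should be dated and recorded as made without sight of outcomes by arm.
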